Characteristics, patterns and outcomes of patients who present with head injuries to one tertiary emergency department: multi-method study

CONFIDENTIAL

This document is confidential and the property of Royal North Shore Hospital Northern Sydney Local Health District

No part of it may be transmitted, reproduced, published, or used without prior written authorisation from the Institution.

STATEMENT OF COMPLIANCE

This document is a protocol for a clinical research study. The study will be conducted in compliance with all stipulations of this protocol, the conditions of ethics committee approval, the NHMRC National Statement on Ethical Conduct in Human Research (2007) and the Note for Guidance on Good Clinical Practice (CPMP/ICH-135/95)

PROTOCOL SYNOPSIS

Title	Characteristics, patterns and outcomes of head injuries presenting to one tertiary emergency department (ED).
Objectives	
Primary: the incidence of patient presentations to Royal North Shore Hospital (RNSH) ED with head injury.
 
Secondary: to follow up on patient journey at 10-14 days and four weeks from discharge. To review; the discharge process from ED, patient symptoms/progress, community management and the need for further management.

Study Design	Observational Cohort Study
Planned Sample Size	
Phase 1 medical record audit: 36 months (2019/2020/2021) of electronic medical record (eMR) data ~267,000 patients.
 
Phase 2 telephone interview: anticipate recruitment rate of 150 patients.

Selection Criteria	
Phase1: what is the incidence of head injuries and does the pandemic and social isolation impact or change the rate of presentations to ED?
 
Phase 2: patients up to 30 years of age who present to the ED with a head injury then discharged home or admitted to the ward.

Study Procedures	
Identify suitable patients on presentation to ED, review eMR diagnosis/documentation, fill excel data spreadsheet, two follow up phone call interviews (at 10-14 days and four weeks from day of discharge). Qualitative study, data collection including a retrospective record review.
 
Phase 1: retrospective 36 month eMR audit to examine the incidence, characteristics and patterns of patients that present with a head injury before and during the Covid-19 pandemic.
 
Phase 2: telephone follow up of patients (up to 30 years of age) that present to the ED with a head injury and discharged home or admitted to the ward.

Statistical Procedures	
Sample Size Calculation: phase 1 presentations for 2019 was approx. 89,000 and head injury accounts for 5%; phase 2 estimated at 350 patients. Based on an 80% response participation rate the sample size is estimated to be 280 (up to 30 years of age) participants.
 
Analysis Plan: review data gained from pre-completed excel spreadsheet and information gained from phone call interviews

Duration of the study	
November 2020 – December 2023
 
Retrospectively eMR audit: 1st January 2019 – 31st December 2021

1. Study Management

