4.3 Number of Participants

Phase 1: N=267,000. All patients (up to 30 years of age) presenting to the RNSH ED will be reviewed for evidence of signs and or symptoms of head injuries over a 36 month period to compare pre and during the COVID-19 pandemic. The annual presentation is approx. 89,000 it is anticipated that 5% may have experienced head injury and/or displaying signs/symptoms of head injury. So the anticipated sample size would be approx. 4,450 patients.

Phase 2: N=280. All patients presenting to the RNSH ED and discharged home or admitted to the ward will be invited to participate in a telephone interview. Stratified prospective sample of patients (up to 30 years of age) who present to ED are diagnosed with head injury and discharged home or admitted to the ward. Recruitment will begin from the in 1st January 2021 – 31st December 2021.

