5. PARTICIPANT ENROLLMENT AND RANDOMISATION

5.1 Recruitment

Patients up to the 30 years of age have been included in the study as this patient cohort are more likely to be involved in team contact sports and less likely to have co-morbidities. Posters will be positioned in all areas of the ED (with the exception of the resuscitation bays).

Phase 1: A 36 month (1st January 2019 - 31st December 2021) eMR audit of all patients (up to 30 years of age) presenting to ED will be reviewed for evidence of head injuries. Limitation of snowmed diagnostic codes will require review of all emergency presentations eMR to determine patients that have presented or been discharged with signs/symptoms of head injury or concussion. Review of eMR will be undertaken by the lead researcher to identify participants meeting inclusion criteria for phase 1. Due to the large number of patient records being accessed data for 2021 will only be accessed in early 2022 and as such, will be retrospective in nature.

Phase 2: A 12 month (1st January – December 31st 2021) prospective study of patients (up to 30 years of age) who present to ED with a head injury will be included in the study. The aim of the telephone interview is to collect data after the patient has been discharged from the ED. To obtain information from the patient such as; feedback on the discharge process, ongoing symptoms, return to sport, school, study or work or the need for further medical review.

For phase 2 potential participants will identified then recruited by clinicians or the emergency research volunteers, who will seek written consent whilst they are in the ED to participant in two telephone interviews.

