All patients will have the opportunity to opt out of the study without any impact on care practices. Randomisation will occur 1:1 ratio for patients < 16 years of age and patients > 16 years of age to identify 20 participants per week, who will be contacted 10-14 days post injury and then four weeks post discharge. Telephone interviews will be conducted by either ED research volunteers, the lead researcher or associate researchers from the RNSH ED Office. Prior to the commencement of the telephone interview each patient/parent/carer on contact will be again given the opportunity to opt out and verbal consent will be obtained. Each participant will be invited to select an interview schedule time suitable for them. Potential participants will only be contacted three times and if unable to be contacted will be considered as declining to participate in the study. Potential participants will only be contacted between the hours of 0800am until 0600pm (Monday – Friday).

All emergency clinicians will be briefed about the study via email, posters and short in-services.

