8.1 Sample Size Estimation

This is an observational study not requiring a powered sample.

Phase 1 medical record audit: 36 months of ED data characterising approximately 267,000 patients. All data is routinely collected and will be obtained through eMR

Phase 2 telephone interview: anticipate recruitment rate 280 patients or until data saturation is reached.

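### The Phase 2 sample size is given as 150 in one place and 280 elsewhere, and a draw of 20 participants per week does not fit 280 over the 12-month window

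*Protocol*

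**What the plan says.** The protocol states the size of the telephone-interview phase in four places.

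- **Synopsis, Planned Sample Size:** "Phase 2 telephone interview: anticipate recruitment rate of 150 patients".
- **Synopsis, Statistical Procedures:** "phase 2 estimated at 350 patients", followed by "Based on an 80% response participation rate the sample size is estimated to be 280 (up to 30 years of age) participants".
- **Section 4.3:** N is 280.
- **Section 8.1:** "Phase 2 telephone interview: anticipate recruitment rate 280 patients or until data saturation is reached". Apart from the saturation clause, this is almost the wording of the Planned Sample Size row, with 280 in place of 150.

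Two further statements fix the pace and the period. Section 5.1 describes a 1:1 selection by age (under and over 16 years) "to identify 20 participants per week, who will be contacted 10-14 days post injury and then four weeks post discharge". On timing, Section 4.3 says "Recruitment will begin from the in 1st January 2021 – 31st December 2021", and Section 5.1 likewise describes a 12-month prospective study over the same calendar year.

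Nothing in the protocol links 150 to 280, or says how a weekly draw of 20 is meant to produce either number over 12 months.

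**The concern.** A protocol should give one recruitment target, and the operating instructions should lead to it. Here two rows of one synopsis table disagree by a factor of almost two, and the weekly selection rule in Section 5.1 points to a third scale of study altogether.

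The consequences are practical. Staff following Section 5.1 cannot tell whether to keep selecting 20 a week to the end of December, and so go far beyond the target, or to stop once the target is met, and so leave most of the planned year unsampled. The ethics committee sees a different number of participants depending on which row it reads. The workload, at two calls per participant in an unfunded study, also differs several-fold between the readings.

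**Working it through.** **Inputs, all from the protocol**

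- 350 patients and 80% participation: synopsis, Statistical Procedures.
- Target 280: the same row, and Sections 4.3 and 8.1.
- Target 150: synopsis, Planned Sample Size.
- Draw of 20 per week: Section 5.1.
- Window 1 January to 31 December 2021, taken as 52 weeks: Sections 4.3 and 5.1.

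**Step 1. Reproduce the plan's own figure.** 350 × 0.80 = 280. In reverse, 280 / 0.80 = 350. The derivation is correct.

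**Step 2. Test whether 150 follows from anything stated.**

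- 150 / 350 = 43%, not 80%.
- 150 / 280 = 54%, not 80%.
- Applying 80% a second time gives 280 × 0.80 = 224, not 150.
- Inflating 150 for 80% participation gives 150 / 0.80 = 187.5, which appears nowhere.

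No combination of the stated inputs gives 150.

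**Step 3. Weekly draw run over the full window.**

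- Selected: 20 × 52 = 1,040.
- Interviewed at 80%: 1,040 × 0.80 = 832.
- Against the target: 1,040 / 280 = 3.7 and 832 / 280 = 3.0.

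**Step 4. Weekly draw stopped at the target.** Weeks needed = number to select / 20, counted from 1 January 2021.

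| Reading of the 20 | Number to select | Weeks | Share of 52 weeks | Reached about |
|---|---|---|---|---|
| All 20 take part | 280 | 280 / 20 = 14.0 | 27% | 9 April 2021 |
| 80% of the 20 take part | 350 | 350 / 20 = 17.5 | 34% | 3 May 2021 |

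**Step 5. Draw that would fit the target and the window.** 350 / 52 = 6.7 selected per week, giving 280 / 52 = 5.4 interviewed per week. A whole-number draw of 7 gives 7 × 52 = 364 selected and 364 × 0.80 = 291 interviewed, close to the target.

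**Step 6. Alternative reading of the 20.** If 20 were meant in each of the two age groups, the draw would be 40 per week. The target would then be met in 280 / 40 = 7 to 350 / 40 = 8.75 weeks, so the mismatch would be larger.

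**The case against.** The strongest reply is that only 150 and 280 are printed as sizes. The 1,040 is a product of a weekly rate and a calendar window, and it assumes the draw is met every week from 1 January. Section 5.1 describes selection, which is followed by a further chance to opt out, verbal consent and a limit of three contact attempts, and 20 may have been intended as a ceiling. This stands in part: 1,040 is an implied throughput, not a stated target. But the text gives 20 as the number to identify and does not call it a maximum. Allowing for 80% participation still leaves 832.

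It may also be said that 20 a week is unattainable. Section 4.3 expects about 4,450 head-injury patients a year, or 4,450 / 52 = 86 a week. That section attaches the figure to patients up to 30, although the 89,000 behind it appears to be all presentations, and the eligible share is not given. On the assumption that the 86 covers all ages, 20 a week needs an eligible share of about 20 / 86 = 23%. The documents do not settle this, and if the share is lower, the 20 itself needs correcting.

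Three stronger readings are tempting but not supported.

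- **Lost winter months.** A reader might infer that the cohort will close by April or May and miss the winter sports season. Closure depends on full weekly yield and on a stop at 280. The protocol only anticipates 280 and twice names a 12-month window. It does not mention season, plans no seasonal comparison in Phase 2, and admits any head injury.
- **Data saturation as a defect.** A reader might want the saturation clause in Section 8.1 removed. Section 8 describes semi-structured interviews analysed thematically, and saturation is an ordinary stopping idea for such work. The multivariate analysis of compliance is planned only if the data allow. The clause does not reconcile 150 with 280, but it is not an error.
- **Lost precision.** A reader might compare confidence-interval widths at the different sizes. Section 8.1 says no powered sample is required, and no precision target is set for any Phase 2 proportion, so such widths would not show harm to a planned inference.

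**Conclusion.** The point holds as an internal inconsistency in two parts.

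First, the Phase 2 size is 150 in one synopsis row and 280 in three other places. This needs no assumption. The 280 is the only figure with a derivation, and the derivation reproduces, so the 150 is the figure out of line.

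Second, the target of 280, the draw of 20 per week and the 12-month window cannot all be followed. Either selection overshoots the target about 3 to 3.7 times, or the target is met in roughly the first quarter to third of the year. The two outcomes are alternatives and cannot both occur. The first assumes that 20 is met every week for 52 weeks. The second assumes that 20 is met from 1 January and that recruitment stops at the target, which the protocol does not state.

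No test or power claim rests on the 150, and the protocol does not show that the resulting data would be biased.

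**What to change.** 1. In the Planned Sample Size row of the synopsis, replace 150 with 280, and say there that this is 80% of 350. The row then agrees with Statistical Procedures and with Sections 4.3 and 8.1.
2. In Section 5.1, make the weekly draw consistent with 280 over the whole of 1 January to 31 December 2021. One option is about 7 selected per week (350 / 52 = 6.7). Another is to keep 20, state that it is a weekly maximum, and state that selection is spread over all 12 months. In either case, say whether the weekly number counts people selected or people interviewed, and whether it is the total across both age groups.

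The cost is a wording change in two places, submitted to the ethics committee as an amendment under Section 10.2. The target of 280 is unchanged, so no additional participants are needed. Spreading selection means that recruitment runs the full year, which the protocol already plans.

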1.3 Statistician (if applicable)

Mainly descriptive exploratory data will be presented and summarised using frequencies and percentages. Basic inferential statistics will be used for group comparisons to be undertaken depending on data distribution. Normally distributed data will be analysed using t test and anova. Non normally distributed data will use parametric testing Mann Whitney, Kruskal Wallis, Chi Square and Fischer exact depending on data type and coding.

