4.2 Study Design

This is an observational Cohort Study of people that present to a major tertiary hospital with a head injury. The study comprises of two phases;

Phase 1 medical record audit: To explore the characteristics, patterns and outcomes of people (up to 30 years of age) that present with signs and symptoms of head injuries to one major tertiary referral hospital ED comparing pre and during the COVID-19 pandemic.

Phase 2 telephone interviews: Stratified prospective sample of patients (up to 30 years of age) who present to ED and diagnosed with head injury, given written and verbal discharge education / information / instructions and followed up appropriately in the community using telephone interview.

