4.6 Primary and Secondary Outcome Measures

Primary outcome:

- To explore the characteristics, patterns and outcomes of patients that present with head injuries to one major tertiary referral hospital ED.
- How are head injury patients managed in the community and the need for further management.

Secondary outcomes:

- To compare data both pre and during the COVID-19 pandemic
- Identification of evidence based concussion assessment and management in the ED
- How were head injury patients managed in the ED
- Identification of the type and appropriateness of discharge information, education and instructions
- What discharge instructions were provided for commencing post head injury activities such as return to school, work and sporting activities
- What were the patterns of community referrals

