8. STATISTICAL METHODS

The retrospective eMR audit does not require a power calculation as we are not testing an intervention but seeking to explore and characterise service data. Phase 1 data to be collected includes: patient demographic information (age, gender, etc.) and clinical information (for example date/time of arrival, triage category, reason for ED presentation, assessment and diagnostic code, discharge summary, nursing documentation, community referrals, length of stay, disposition, ED clinical space) to determine patients that have presented or discharged with signs/symptoms of head injury or concussion pre COVID 19 and during the pandemic.

For the descriptive exploratory study quantitative data will be presented using descriptive statistics and summarised using frequencies and percentages. Examining for central tendency means, standard deviation (normally distributed data), or median and interquartile range (non-normally distributed data) will be analysed. For continuous data comparison will be conducted using T test and Chi square will be used for categorical data. If the data allows (there are sufficient observations and the distribution of data is appropriate) we will conduct multivariate analyses to explore the determinants of patient compliance with ED discharge information. Quantitative data analysis will be performed using SPSS v.21 and Excel for data cleaning, mining and summaries of data sets. All data will be de-identified.

For Phase 2 involves qualitative interview data obtained from semi-structured telephone interviews. Data to be collected includes: patient demographic information (age, gender, etc.), history including mechanism of injury, signs/ symptoms of concussion, management in ED and follow up plan. All responses provided by patients or their persons responsible will be analysed and organised thematically and stored and managed using NVivo™ v12. Thematic analysis will be guided by Gibbs's (2007) framework which includes: 1) transcription and familiarisation; 2) code building; 3) dis/confirmatory theme development; and 4) data consolidation and interpretation. This framework provides a systematic approach for interpretation (Lichtman, 2010, Brodie and Irving, 2007). The investigators will discuss and review emerging coding and themes.

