8.2 Statistical Analysis Plan

We will conduct measures of frequency and central tendency to analyse the collected data set. Incomplete data sets will not be used in our statistical analysis. We will report the number of incomplete data sets collected.

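### Phase 1 compares outcomes before and during the pandemic with unadjusted tests only, so a shift in age or triage mix can be read as a change in outcome or care

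*Protocol*

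**What the plan says.** Section 4.2 of the protocol sets Phase 1 up to explore characteristics, patterns and outcomes of people up to 30 years of age who "present with signs and symptoms of head injuries to one major tertiary referral hospital ED comparing pre and during the COVID-19 pandemic". Section 4.6 lists as a secondary outcome "To compare data both pre and during the COVID-19 pandemic". A separate bullet in that list is "How were head injury patients managed in the ED", with no period attached.

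The methods appear in three places:

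- Section 1.3: "Basic inferential statistics will be used for group comparisons to be undertaken depending on data distribution". It then lists the t test, ANOVA, Mann-Whitney, Kruskal-Wallis, chi-square and Fisher's exact test.
- Section 8: "For continuous data comparison will be conducted using T test and Chi square will be used for categorical data".
- Section 8.2: "We will conduct measures of frequency and central tendency to analyse the collected data set".

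The only multivariable work is in Section 8. It depends on the data being sufficient and serves another question: "we will conduct multivariate analyses to explore the determinants of patient compliance with ED discharge information".

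The Phase 1 data list in Section 8 includes age, gender, triage category, length of stay, disposition and community referrals. The exclusions for triage category 1 and for the resuscitation area (Section 5.2.2) apply to Phase 2, so the audit spans all triage categories and all ages up to 30.

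**The concern.** Outcomes among people who attend depend on who attends. Admission and length of stay can be expected to vary with age and triage category, and Phase 1 pools both. A chi-square or t test of 2019 attenders against pandemic attenders therefore mixes two things: a change in the composition of attenders, and a change in what happened to comparable attenders. The tests named cannot separate them.

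This differs from the question of how many people presented. Even with a perfectly measured presentation rate, a crude contrast of outcomes among attenders would still carry any difference in case mix.

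Two errors are possible. The study could report that admissions or length of stay changed when nothing changed within any age or acuity group. Or a real change could be offset by a mix shift and go unseen. Section 11 anticipates that the findings will lead to policy change for discharge and care. It does not tie that to the pandemic contrast, but a statement that outcomes changed in the pandemic would be among the results available for that use.

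**Working it through.** **The protocol's own counts.** Section 4.3 gives about 89,000 presentations a year and a 5% head-injury share.

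- 0.05 × 89,000 = 4,450, which reproduces the stated figure. It is one year's count and is taken from all ages.
- 3 × 89,000 = 267,000, which reproduces the audit total. At 5% this is 13,350 head injuries over 36 months.

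The protocol gives no age shares, admission risks, significance level or pandemic start date. Everything below is therefore an illustration on assumed inputs.

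**Illustration by age.** Assume:

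- admission is 5% under 16 and 15% at 16-30, the same in both periods;
- the under-16 share is 60% before the pandemic and 50%, 45% or 40% during it;
- the periods are 2019 against 2020-21, a 1:2 split;
- the test is two-sided at 5% (critical z 1.96).

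Crude admission = s × 0.05 + (1 − s) × 0.15, where s is the under-16 share.

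- Before: 0.60 × 0.05 + 0.40 × 0.15 = 0.090
- During, s = 0.50: 0.025 + 0.075 = 0.100
- During, s = 0.45: 0.0225 + 0.0825 = 0.105
- During, s = 0.40: 0.020 + 0.090 = 0.110

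The true difference within each age group is zero. The pooled two-proportion statistic is z = (p1 − p0) / √[p(1 − p)(1/n0 + 1/n1)]. For s = 0.45 the pooled p is (0.090 + 2 × 0.105)/3 = 0.100. With 4,450 vs 8,900 the standard error is √[0.09 × (1/4,450 + 1/8,900)] = 0.00551, so z = 0.015/0.00551 = 2.72.

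The count of 4,450 a year covers all ages, so it is an upper bound for a cohort aged up to 30. If 40% of cases are 30 or under (assumed), the counts are 0.40 × 4,450 = 1,780 and 0.40 × 8,900 = 3,560.

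| Under-16 share during | Spurious difference | z, 1,780 vs 3,560 | z, 4,450 vs 8,900 |
|---|---|---|---|
| 50% | 1.0 point | 1.17 | 1.84 |
| 45% | 1.5 points | 1.72 | 2.72 |
| 40% | 2.0 points | 2.26 | 3.58 |

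**Masking.** Suppose admission really fell by 1.5 points in each age group, to 3.5% and 13.5%, while the under-16 share fell to 45%. Crude admission during the pandemic is 0.45 × 0.035 + 0.55 × 0.135 = 0.090, identical to the 0.090 before. The crude test would be looking at no difference at all.

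**Illustration by acuity.** Assume admission is 40% at high and 10% at low acuity in both periods, and the high-acuity share rises from 20% to 25%, 30% or 35%.

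- Before: 0.20 × 0.40 + 0.80 × 0.10 = 0.160
- During: 0.175, 0.190 and 0.205, so the spurious differences are 1.5, 3.0 and 4.5 points
- Chance that the crude test is significant: 0.24, 0.69 and 0.96 with 4,450 patients in total; 0.59, 0.99 and 1.00 with 13,350 in total (the all-age count)

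With 30% in place of 40% at high acuity, the chances are 0.14, 0.41 and 0.74 (4,450) and 0.34, 0.86 and 0.995 (13,350). For a rise from 20% to only 22%, they lie between 0.05 and 0.14 across both sets of risks and both totals. The acuity-stratified difference is zero throughout.

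**The case against.** The strongest case against has five parts.

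1. *The study is mainly descriptive.* Section 1.3 says so, and Section 8 describes the audit as exploring service data. For describing patients and service load, the crude contrast is the right quantity. Age and triage are collected, so a mix shift could be seen beside a crude outcome table. This stands in part: a reader might infer that a mix shift is bound to be misread, but the documents support only that it can be. A table of age and triage still does not show how much of a crude difference the shift explains.

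2. *The protocol does not predict a change in who attends.* A reader might infer that it does. Sections 2.2 and 4.2 do not support that: the research question is whether the presentation rate changes, asked openly, with nothing said about composition. This stands, so the concern is conditional on a mix shift occurring.

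3. *A period comparison of ED management is not spelled out.* A reader might infer one from Section 4.6, where management and the pandemic comparison are neighbouring bullets. This stands. Section 4.2 does attach outcomes to "comparing pre and during the COVID-19 pandemic", but management comes in only through the general wording about comparing data. Disposition and length of stay are likewise taken here from the Section 8 data list as natural examples of outcomes.

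4. *The numbers are assumed, and the larger ones use an all-age count.* This stands. At 1,780 vs 3,560, only the largest of the three age shifts passes 1.96. A reader might take significance at 4,450 vs 8,900 as the likely result, but that count is not restricted to patients up to 30. The bias in the estimate is the same at any sample size.

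5. *Choice of covariates is commonly left to an analysis plan.* That is true of covariate detail. Here, though, the protocol names its tests in Sections 1.3 and 8 and assigns its only multivariable model to a different outcome. It has stated a method for group comparisons, and that method is crude.

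**Conclusion.** The concern holds as a conditional one. The protocol compares outcomes between two calendar periods, names only unadjusted tests for group comparisons, and reserves its single conditional multivariable analysis for compliance with discharge information. No section adjusts, stratifies or standardises the period comparison, although the variables needed are collected.

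If age or triage mix differs between periods, the crude contrast is biased. The documents do not allow the bias to be sized. The assumed age shifts give 1.0 to 2.0 points of admission, and the assumed acuity shifts of 5 to 15 points give 1.0 to 4.5. Whether that reaches significance depends on the size of the shift and on how many cases are 30 or under, which the protocol does not state. With a small shift it usually would not.

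The verdict does not extend to the presentation rate, or to the description of age, triage and other characteristics, where a change in who attends is itself the finding. For ED management it applies only if management is in fact compared by period.

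**What to change.** Add one paragraph to Section 8 and bring Section 1.3 into line with it:

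- Keep the crude tables and tests as the description of attenders in each period.
- For each comparison of an outcome before and during the pandemic (and of ED management, if compared by period), also report a difference adjusted for age, gender and triage category, with a 95% CI beside the crude one. Use either a regression with period and these covariates, or direct standardisation to the pre-pandemic age-by-triage mix.
- Base any statement that outcomes or care changed on the adjusted result.

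Age, gender and triage category are already on the Phase 1 data list, and the planned software can fit the model. The cost is a little more analysis and somewhat wider intervals where age-by-triage cells are sparse. Adjustment for these three variables will not remove every difference in case mix. Mechanism of injury, for example, may also shift, and the report should say so.
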